### Exclusion Criteria:

- Patients not undergoing leak closure after incomplete LAAC
- Patients unable to complete 45-day follow-up imaging for reevaluation of LAA leak
- Patients unable to consent

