## **Secondary Endpoints:**

1. To compare the reduction/rates of TE events and procedure-related complications (DRT, pericardial effusion/cardiac tamponade, or CVA/TIA) in patients after successful PDL closure with any of the three closure modalities
  - a. Periprocedural complications occurring from Postoperative day #0 – day 7
  - b. Delayed procedure-related complications and adverse events within 90 days of procedure

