## **Statistical Analysis:**

Continuous variables will be summarized using mean and standard deviation, while categorical variables will be summarized as counts and percent of the total. Comparison analysis between groups will be made using Kruskal-Wallis tests for nonparametric data sets as appropriate. Leak sizes were measured initially and then via postprocedural follow-up, with overall rates of closure, minimal-mild leaks, and clinically significant leaks listed with associated p-values. All tests were two-tailed, and a  $P$  value less than 0.05 was considered statistically significant. All analyses were performed using SPSS Statistics version 28.0.0.0 (IBM).

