## **Data/Variable Points for Collection:**

- Age
- Sex
- Height
- Weight
- BMI
- Diabetes (y/n)
- Smoking (y/n)
- Dyslipidemia (y/n)
- Prior stroke/TIA (y/n)

- Prior deep venous thrombosis/pulmonary embolism (y/n)
- Ejection Fraction
- History of CAD (y/n)
- Congestive heart failure (y/n)
- Chronic Kidney Disease (y/n)
- Type of Atrial Fibrillation (paroxysmal, persistent, permanent)
- Baseline antithrombotic regimen (aspirin, clopidogrel/prasugrel/ticagrelor, warfarin, direct oral anticoagulant, heparin)
- TIA/stroke after Watchman
- History of major bleeding
- High Fall risk (y/n)
- Previous major bleeding (y/n)
- Previous minor bleeding (y/n)
- Thromboembolism while on oral anticoagulant
- CHA2DS2-VASc Score
- HAS-BLED Score
- Time passed since LAA closure (months)
- Type of LAA Closure (watchman/watchman FLX, amulet, lariat, surgical ligation, atriclip)
- Device Size (if applicable)
- Thrombus on device (y/n)
- Peri-device/central leak size in mm
- Acute success (end of procedure closure) (y/n)
- Procedure duration (minutes)
- Flourosopy time (minutes)
- Contrast usage (mL)
- Hospital length of stay
- Type of procedural anesthesia (general vs light sedation vs local)
- Procedural imaging (TEE, ICE, or both)
- Devices attempted
- Devices deployed
- Combination procedures (combined AF ablation, or LAA occlusion + AF ablation)
- Size/number of devices (plugs/coils)
- Major procedural complications from postoperative day 0-7: stroke, TIA, air embolism, myocardial infarction, cardiac tamponade, device embolization, ventricular tachycardia
- Minor procedural complications from postoperative day 0-7: pericardial effusion
- Complications seen within 90 days of the procedure: cardiovascular death, non-cardiovascular death, stroke/TIA, pericarditis
- Follow-up transesophageal echocardiogram time (months)
- Size of leak at follow up (in mm)
- Follow-up time
- Follow up antithrombotic regimen

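### The delayed-complication endpoint has no lower bound or event timing, and follow-up is assured only to 45 days, so early stroke/TIA can be reported as delayed and 90-day rates can be understated

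*Combined protocol and SAP*

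**What the plan says.** All references are to the combined protocol and SAP.

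- **Secondary Endpoints** compares thromboembolic events and procedure-related complications between modalities in two parts: (a) "Periprocedural complications occurring from Postoperative day #0 – day 7" and (b) "Delayed procedure-related complications and adverse events within 90 days of procedure".
- **Data/Variable Points for Collection** records complications by window. The early fields are "Major procedural complications from postoperative day 0-7: stroke, TIA, air embolism, myocardial infarction, cardiac tamponade, device embolization, ventricular tachycardia" and "Minor procedural complications from postoperative day 0-7: pericardial effusion". The later field is "Complications seen within 90 days of the procedure: cardiovascular death, non-cardiovascular death, stroke/TIA, pericarditis". No field records the date or day of an event. "Follow-up time" is listed for each patient, without unit or definition, separately from the timing of the follow-up TEE.
- **Exclusion Criteria** removes "Patients unable to complete 45-day follow-up imaging for reevaluation of LAA leak". No section requires observation to day 90.
- **Statistical Analysis** says that "categorical variables will be summarized as counts and percent of the total". It mentions no censoring, no person-time, and no rule for patients with short follow-up.

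**The concern.** There are two separate weaknesses in the same endpoint.

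**Overlap.** The label of (b) suggests a period after the periprocedural one, but its stated limits include days 0–7. The 90-day data field does not carry the word *delayed* at all, so an abstractor who follows it would enter a day-3 stroke there as well as in the early field. That event would then appear under a delayed heading. If a reader or analyst adds (a) and (b), or treats them as consecutive periods, it is counted twice.

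**Unobserved time.** A patient needs to be followed only to the 45-day image to be eligible. With a percent of the total and no censoring rule, a patient last seen on day 50 stays in the denominator, with no event, to day 90. This lowers the reported risk. The study pools centres that use different modalities, so if follow-up length differs by centre, the loss falls unevenly on the groups being compared.

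Few events are expected, so one event misplaced or missed is a noticeable share of the result.

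**Working it through.** The plan has no figure of its own to reproduce. The Sample Size section gives a total of 160 with no event rate, power, allocation or dropout. Every rate and loss fraction below is an assumption, used only to show scale.

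**1. Which complications can be recorded in both windows?**

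| Complication | Day 0–7 fields | 90-day field |
|---|---|---|
| Stroke/TIA | yes | yes |
| Air embolism, MI, tamponade, device embolization, VT, pericardial effusion | yes | no |
| Cardiovascular death, non-cardiovascular death, pericarditis | no | yes |

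Only stroke/TIA overlaps. Comparing the two fields would flag a patient with an early event, but could not show whether a second event followed after day 7.

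**2. Effect of adding (a) and (b).** Let R be the true 90-day stroke/TIA risk and f the share of those events on days 0–7. The sum is R(1 + f). With R = 2% and f = 25%, 50%, 75%, it is 2.5%, 3.0%, 3.5% instead of 2.0%. With R = 5%, it is 6.25%, 7.5%, 8.75%. In counts, one event entered twice turns 2/160 = 1.25% into 3/160 = 1.9%. The endpoint is restricted to patients with successful closure, so the real denominators would be smaller than 160.

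**3. Effect of unobserved time.** Days 46–90 are 45 of the 91 days from 0 to 90 (49%). Let q be the share of patients last seen at day 45.

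- *Constant hazard, low risk:* relative understatement = q × 45/90. For q = 30%, this is 0.30 × 0.5 = 15%.
- *Early clustering, with the other events spread evenly over days 8–90 (83 days):* relative understatement = q × (1 − f) × 45/83.

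| q | f = 25% | f = 50% | f = 75% |
|---|---|---|---|
| 10% | 4.1% | 2.7% | 1.4% |
| 30% | 12.2% | 8.1% | 4.1% |
| 50% | 20.3% | 13.6% | 6.8% |

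- *Unequal follow-up, constant hazard:* if q is 60% in one group and 10% in another with the same true risk, the understatements are 30% and 5%. The apparent risk ratio is 0.70/0.95 = 0.74. This pair of loss fractions is invented to show direction. The documents give no follow-up by modality.

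**4. Absolute scale.** At 2–5 events per 100 patient-years, 160 × 90/365 = 39.5 patient-years give 0.8–2.0 events. A 15% understatement is then 0.12–0.30 of an event. At a 90-day risk of 2–5%, 160 patients give 3.2–8.0 events, about 1–3 per modality if split equally.

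**5. Deaths.** Read literally, the exclusion removes anyone who dies before the 45-day image. Countable deaths then fall almost entirely after it. If they are spread evenly over that later period, 30% of patients last seen at day 45 would hide about 30% of countable deaths.

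**The case against.** A reader might infer that the 90-day rates do double-count early events, and that the plan classes unseen patients as event-free. The documents support neither as a stated fact.

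- A cumulative day 0–90 rate counts a day-3 stroke once. Double-counting needs (a) and (b) to be added or read as separate periods, and no section plans that. The contrast between periprocedural and delayed can also be read as meaning after day 7. This stands: the defect is an ambiguity that permits the error.
- The sentence on percentages is a generic descriptive rule. It does not say which total applies or how short follow-up is handled. This stands in part: counting such patients as event-free is the default result of the rule, not an instruction.
- "Follow-up time" is collected, so patients seen for less than 90 days could be identified. This also stands, but the field is undefined, the analysis makes no use of it, and without event timing it cannot support a time-to-event estimate.
- The two harms cannot both be at full size. Under constant hazard, days 0–7 hold 8/91 = 9% of events, so of 0.8–2.0 expected events only 0.07–0.17 would be early. If events cluster early, double entry matters more and the under-count shrinks. This is correct, and step 3 of the working shows the range.
- Kaplan–Meier does not by itself give an unbiased 90-day risk, because inclusion depends on reaching the 45-day image. This is also correct, and the fix has to address it. With so few events, the gain over a proportion among patients with known day-90 status is modest.

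**Conclusion.** The point holds in a conditional form. As written, (b) can include day 0–7 stroke/TIA under a delayed label, and that event would be counted twice if (a) and (b) are added or read as separate periods. No other listed complication is affected. By default, patients last seen between day 45 and day 90 count as event-free.

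The size cannot be determined from the documents. About 15% relative understatement follows from a constant hazard and 30% last seen at day 45. With 25–75% of events on days 0–7, the same loss gives 12% down to 4%. In absolute terms this is a fraction of an event to about one event. The 0.74 ratio shows only the direction that unequal follow-up could push the comparison, and is not an estimate for this study.

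This concerns a secondary endpoint and does not undermine the study. It does affect a named comparison between modalities and is cheap to put right.

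**What to change.** 1. Define (b) as days 8–90. Alternatively, label it cumulative from day 0 to day 90 and state that it is never added to (a). Word the 90-day data field to match.
2. Record the number of days from procedure to each event, and define "Follow-up time" as days from procedure to last contact. Intervals in days need no calendar dates, so they fit the plan to de-identify early. They should be abstracted before that step, since timing may be hard to recover afterwards.
3. Report, for each modality, the number observed to day 90.
4. Replace the percent of the total for this endpoint with a Kaplan–Meier estimate, or a cumulative-incidence estimate with death as a competing event, with a 95% CI for each modality.
5. State that the estimate is conditional on completing the 45-day image. Alternatively, for the safety endpoint, also count early deaths and events in treated patients who did not reach that image.

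The cost is two intervals per chart and a few sentences of analysis text. The downside is minor abstraction time and a slightly higher reported 90-day rate.

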## **Informed Consent:**

Given that this study was observational and retrospective in design, no informed consent was obtained or required. Patients who met inclusion/exclusion criteria were de-identified and added to word documents/excel spreadsheets.

## **Data storage/Confidentiality:**

Data will be collected in word documents, PDFs, and excel sheets. Data recorded on the worksheets will be entered into a secure password protected computer database by the research staff at corresponding heart institutes/cardiac centers. Only investigators involved in the study will have access to the data. All data will be reported in aggregate form and no names will be used for any publications resulting from the research. De identification of data will be done at the earliest.

## **Sample Size:**

We will plan to aim for a total size of 160 patients in total among all three modalities.

## **Statistical Analysis:**

Continuous variables will be summarized using mean and standard deviation, while categorical variables will be summarized as counts and percent of the total. Comparison analysis between groups will be made using Kruskal-Wallis tests for nonparametric data sets as appropriate. Leak sizes were measured initially and then via postprocedural follow-up, with overall rates of closure, minimal-mild leaks, and clinically significant leaks listed with associated p-values. All tests were two-tailed, and a  $P$  value less than 0.05 was considered statistically significant. All analyses were performed using SPSS Statistics version 28.0.0.0 (IBM).

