## **2. Objectives:**

### Primary Objective:

Our main objective is to collect data from multiple different centers that use different modalities to currently treat either central or peri-device leaks that occur after incomplete LAA closure, and compare each modality in their efficacy and safety outcomes.

Primary Outcome: To compare the efficacy of the three current methods of PDL closure modalities in patients with prior incomplete LAAC.

Secondary Outcome: To compare the rates or reduction of rates of thromboembolic events and procedure-related complications in patients after successful PDL closure with any of the three closure modalities.

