## **3. Research Methods and Statistical Considerations:**

### **Research Methods:**

This will be a multi- center retrospective observational comparison study.

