### **Study Population:**

All patients at risk for stroke or thromboembolism that demonstrated any degree of the significant leak on follow up TEE imaging at least 4-6 weeks following either epicardial, endocardial, or surgical LAAC were included in this study population. All patients were evaluated and followed with imaging, and per investigators' respective clinical judgement, then proceeded to have an intervention for leak closure with either detachable embolization coils, vascular plugs/CSO, or RFA.

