### Inclusion Criteria:

- patients at risk for stroke or thromboembolism that demonstrated any degree of the significant leak on follow up TEE imaging at least 4-6 weeks following either epicardial, endocardial, or surgical LAAC
- Patients undergoing any form of eccentric or centric/central leak closure with available modalities (detachable embolization coils, vascular plug/septal/ASD occluders, or RF Ablation). Criteria for this was made based on the judgement of the operator, with no specific cutoffs for leak size, follow-up time from LAAC to leak closure, etc)
- Age greater than 18 years

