### **Primary Endpoints:**

1. To compare the efficacy of the three PDL closure modalities in patients with prior LAAC

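### The primary comparison of the three closure modalities is not randomised, yet only unadjusted tests are planned and nothing corrects for entry leak size

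*Combined protocol and SAP*

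**What the plan says.** Research Methods describes a "retrospective observational comparison study". The Primary Objective is to "collect data from multiple different centers that use different modalities to currently treat either central or peri-device leaks". Under Study Population, patients were managed according to investigators' "respective clinical judgement, then proceeded to have an intervention for leak closure with either detachable embolization coils, vascular plugs/CSO, or RFA". That wording may cover the decision to close as well as the choice of modality; no other allocation rule is given. The Inclusion Criteria leave the decision to the "judgement of the operator, with no specific cutoffs for leak size, follow-up time from LAAC to leak closure".

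The only primary endpoint is "To compare the efficacy of the three PDL closure modalities in patients with prior LAAC".

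The Statistical Analysis section contains descriptive summaries and two statements about comparison. The first is "Comparison analysis between groups will be made using Kruskal-Wallis tests for nonparametric data sets as appropriate". The second is that "Leak sizes were measured initially and then via postprocedural follow-up", with "overall rates of closure, minimal-mild leaks, and clinically significant leaks listed with associated p-values". Tests are two-sided at 0.05. The data list collects entry leak size in mm, follow-up leak size and type of LAA closure, but gives none of them a role in the comparison.

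**The concern.** Without randomisation, the three groups can differ in anything that guided the choice of treatment. Entry leak size is the obvious candidate: it is unrestricted, it is known to the operator, and it could plausibly affect whether the leak closes. Kruskal-Wallis takes no covariates, and crude rates with p-values do not account for baseline differences.

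Two errors are possible. A modality used mainly for small leaks could look better when it is not. A modality that is truly better but used for large leaks could look no different. A baseline comparison might reveal the imbalance, but it would not show how much of the outcome difference the imbalance explains. The Background states that no head-to-head comparison of these modalities exists, so readers would be likely to rely on this one.

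**Working it through.** **Search for adjustment.** No section mentions regression, propensity scores, matching, weighting, stratification, a center effect or a sensitivity analysis for confounding. Measuring leak size before and after is not adjustment: the plan does not say that change is analysed, and the closure rates it lists are crude.

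**Inputs.** From the documents: 160 patients in total (Sample Size) and two-sided 0.05. The 160 has no stated derivation, so there is no figure to reproduce. Everything else below is assumed.

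**Hand-checkable illustration.** Assume 53 patients per group, closure of 90% for smaller leaks and 60% for larger leaks, and no modality effect. With a share *s* of larger leaks, crude closure = 0.90(1 − s) + 0.60s.

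- Shares 30/50/70%: closure 81/75/69%, an extreme-group difference of 12 points. Noncentrality = 53 × (0.06² + 0² + 0.06²)/(0.75 × 0.25) = 2.04. With 2 df the rejection rate is 23%.
- Shares 20/50/80%: closure 84/75/66%, a difference of 18 points. Noncentrality = 53 × (0.09² + 0² + 0.09²)/(0.75 × 0.25) = 4.58. The rejection rate is 47%.
- Shares 50/50/50%: difference 0, rejection rate 5%.

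Simulating the two unbalanced cases gives 21% and 48% for Kruskal-Wallis on closure yes/no, and about 5% after adjustment for leak-size stratum. If larger leaks close in 80% rather than 60%, the crude rates fall to 8% and 9%.

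**Continuous leak size.** Groups of 53/53/54; leak size normal with SD 2 mm, kept within 1–12 mm by redrawing or clipping (the two ends of each range); logit(closure) linear in mm; no true modality effect; 4,000 replicates per scenario unless marked. The crude test is chi-square on closure. The adjusted test is a 2-df likelihood-ratio test from a logistic model containing leak size.

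| Mean leak by modality (mm) | Closure OR per mm | Non-closure | Crude rejects | Adjusted rejects |
|---|---|---|---|---|
| 5/5/5 | 0.67 | 25% | 5% | 5–6% |
| 4/5/6 or 4/5/7* | 1.0 | 25% | 4–6% | 5–6% |
| 4.5/5/5.5 | 0.82 | 25% | 6–7% | 5% |
| 4.5/5/5.5 | 0.67 | 25% | 10% | 5–6% |
| 4/5/6 | 0.82 | 25% | 9–11% | 5–6% |
| 4/5/6 | 0.67 | 25% | 23–27% | 5% |
| 4/5/7 | 0.67 | 25% | 54–59% | 5% |
| 4/5/6 | 0.67 | 10% | 14–15% | 7% |
| 4/5/7 | 0.67 | 10% | 30–34% | 7% |

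*Redraw only: 1,500 replicates at 53/53/54 and 3,000 at 100/40/20.

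At 4/5/6 mm, OR 0.67 and 25% non-closure, crude closure is about 81/75/69%. The median crude odds ratio, third versus first modality, is 0.49–0.51; the true and adjusted values are 1.0. At OR 0.82 the median crude odds ratio is about 0.71. With groups of 100/40/20 and OR 0.67, crude rejection is 22% (4/5/6) and 43% (4/5/7).

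**Would a baseline table help?** Kruskal-Wallis on entry leak size flags the imbalance in 55–59% of runs at 4.5/5/5.5 mm and about 99% or more at 4/5/6 and 4/5/7 mm. The closure test remains uncorrected.

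**Masking.** At 4/5/6 mm, OR 0.67 and 25% non-closure, let the modality used for larger leaks be truly better. Power, crude versus adjusted:

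- log-odds 0/0.4/0.8: 5% versus 27–28% (chosen so that the crude rates nearly cancel)
- log-odds 0/0.6/1.2: 10–12% versus 55%
- log-odds 0/0.3/0.5: 7–8% versus 13%

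**Limits of leak-size adjustment.** Linear adjustment still gives 5–6% when the true effect is a step or hinge at 5 mm (crude 17–80%). It does not cope with other confounders. If LAA closure type also lowers closure (log-odds −0.8) and the ligation/surgical share is 20/20/60% by modality, the leak-adjusted test rejects in 10%; at 5/20/90% it rejects in 25%. Adding closure type brings these to about 6%. With an unmeasured shift of +0.5/0/−0.5 log-odds, the adjusted test rejects in 39–41% (crude 87–89%).

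**The case against.** The strongest objection is that the harm is not demonstrated. Nothing in the documents shows that leak size differs by modality or predicts closure. The high rejection rates need gaps of 1 to 1.5 SD between extreme groups (2/2 and 3/2) and an odds ratio of 0.67 per mm. Under milder imbalance (4.5/5/5.5 mm) the crude rate is 6–10%, and at 10% non-closure it is 5–7%. This stands as a limit on what can be said about size. It does not remove the gap, because an observational comparison cannot take balance for granted.

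Leak size may also not be the main confounder. Center could matter more, since centers use different modalities. Time since closure, combination procedures and follow-up TEE timing are unadjusted too. This is correct, and it is why leak-size adjustment must not be presented as a full solution.

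The plan is also less definite than the check assumes. Efficacy is undefined, the Kruskal-Wallis test is qualified, and the test behind the rates' p-values is unnamed. But no adjusted method is named under any reading. The choice of chi-square hardly matters: Kruskal-Wallis on a yes/no outcome equals the Pearson chi-square times (N − 1)/N = 159/160. Analysing change in leak size might reduce dependence on entry size, but the plan does not specify it and the closure rates would still be crude.

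**Conclusion.** The concern holds. As written, the sole primary comparison cannot separate modality from entry leak size, in either direction. The absence of any adjustment is certain from the text; the size and direction of the resulting bias are not. Under the assumed inputs, false-positive rates run from the nominal 5% (balanced leaks, or leak size irrelevant to closure) to 54–59% (4/5/7 mm, OR 0.67 per mm, 25% non-closure). Leak-size adjustment restores roughly 5–7% only in the best case, where leak size is the sole confounder and is measured without error. The plan should be changed, because the weakness affects its main conclusion and the key baseline variable is already collected.

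**What to change.** In the Statistical Analysis section:

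- Make the main comparison of closure at follow-up a logistic regression on modality, adjusted for baseline leak size as a continuous variable. Report adjusted effects with 95% confidence intervals. Closure is a rate the section already lists; naming it also settles what efficacy means for this analysis.
- Tabulate baseline leak size and LAA closure type by modality. Add closure type as a sensitivity covariate only if the modalities overlap on it and the number of non-closures allows.
- Record center, tabulate it by modality, and state whether the two can be separated.
- Keep the crude rates and Kruskal-Wallis results, labelled unadjusted.
- Word conclusions as associations.

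**Cost.** SAP wording, one model and one added field. Center is not in the data list, but data are entered by staff at each center, so it should be recoverable. Under the assumptions above (OR 0.67, 25% non-closure), intervals on the log-odds scale widen by about 13–14% at 4/5/6 mm and 21% at 4/5/7 mm (SE 0.47 to 0.57). Adding closure type widens them a further 8% (0.519 to 0.563) to 46% (0.531 to 0.773), depending on overlap. With three parameters (two modality contrasts and leak size), 25% non-closure gives 160 × 0.25 = 40 events, or 13 per parameter. At 10% there are only 16, or 5.3 per parameter, and adjusted estimates would be imprecise. Unmeasured selection remains in all cases.

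### No single primary efficacy outcome, scan window or pairwise rule is designated: three leak categories get p-values at 0.05, and the only named test is omnibus

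*Combined protocol and SAP*

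**What the plan says.** The Primary Endpoints section reads "To compare the efficacy of the three PDL closure modalities in patients with prior LAAC". The Primary Objective wants to "compare each modality in their efficacy and safety outcomes". Neither gives a variable, a leak threshold or an assessment time.

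The Statistical Analysis section says leak size is measured initially and again at follow-up, and that results are reported "with overall rates of closure, minimal-mild leaks, and clinically significant leaks listed with associated p-values". On testing it says "Comparison analysis between groups will be made using Kruskal-Wallis tests for nonparametric data sets as appropriate" and that a P "value less than 0.05 was considered statistically significant". It gives no mm boundaries, primary category, pairwise comparison or multiplicity rule.

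Several candidate outcomes exist elsewhere:
- The Background describes the aim in terms of how well the modalities close the leak. It mentions a leak above 5 mm as widely regarded as clinically significant, but the plan does not adopt this as an endpoint definition.
- The data collection list includes end-of-procedure success (yes/no), leak size in mm at follow-up, and time of the follow-up TEE in months.
- The Exclusion Criteria remove "Patients unable to complete 45-day follow-up imaging for reevaluation of LAA leak". This is the only day attached to follow-up imaging, and it is not linked to the endpoint.

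**The concern.** With several candidate outcomes and none designated, the efficacy result can be chosen after the p-values are known. If all three categories are tested at 0.05, a difference in any one could be presented as the finding on efficacy, at about twice the nominal error rate.

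Two further consequences follow. A significant Kruskal-Wallis result says only that the three groups are not all alike. It does not say which modality differs, and that is what the objective asks. The choice of outcome also decides what 160 patients can detect, because power differs sharply between closure, the ordered category and clinically significant leak.

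**Working it through.** **Plan's own figure.** The only design number is the target of 160 in the Sample Size section. It comes with no closure rate, effect size, power or split by modality, so it can be neither reproduced nor shown to be wrong.

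**Inputs from the plan.** Three modalities, three leak categories, two-sided 0.05, total 160.

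**Assumptions, none in the plan.** The categories are mutually exclusive and exhaustive. Arms are 53/53/54 or 80/50/30 (each sums to 160). Splits (closed / minimal-mild / clinically significant, in %) are as in the first table. Modality has no true effect and the arms are exchangeable.

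**Step 1: bounds for three tests.** If independent, 1 − (1 − 0.05)³ = 1 − 0.857 = 0.143. The upper bound is 3 × 0.05 = 0.15. The categories share one total, so the tests are dependent and simulation is needed.

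**Step 2: one Kruskal-Wallis test per category (200,000 null runs per setting).** Chance that at least one has p < 0.05:

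| Split | Arms 53/53/54 | Arms 80/50/30 |
|---|---|---|
| 90/8/2 | 8.9% | 9.0% |
| 80/15/5 | 10.5% | 10.7% |
| 70/20/10 | 11.4% | 11.5% |
| 50/30/20 | 12.1% | 12.1% |

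Pearson chi-square tests with other assumed mixes, and arms 54/53/53 or 100/30/30, give 10.8% to 12.8%. The choice of test is not the problem. For a yes/no outcome, Kruskal-Wallis equals (N − 1)/N times Pearson's chi-square, here 159/160 = 0.994.

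**Step 3: other readings and single tests (arms and splits as in step 2).**
- One 3×3 chi-square test on the whole table: 3.5% to 5.0%.
- One Kruskal-Wallis test on the ordered category: 4.6% to 5.0%.
- Clinically significant leak alone: 2.8% to 4.8% (conservative when the category is rare).

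**Step 4: pairwise comparisons.** Three ungated pairwise tests on the ordered category give 11.2% to 12.3%. Run only after a significant three-group test, they give 4.5% to 5.0%. For closure (Pearson, arms 54/53/53 or 100/30/30) the figures are 11.5% to 12.3% ungated and 4.8% to 5.2% gated. All nine pairwise-by-category tests, ungated, give 23.5% to 27.9%.

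The gate suffices because there are exactly three groups. If all are equal, a false claim must first pass the 0.05 gate. If only two are equal, one true null remains and is tested at 0.05. If all differ, no true null remains.

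**Step 5: power of each single outcome.** One arm follows one pattern and two arms follow the other. Ranges cover both directions, both layouts and each position of the differing arm.

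| Pattern | Closure | Ordered category | Clinically significant leak |
|---|---|---|---|
| 60/35/5 vs 80/15/5 | 0.44–0.71 | 0.39–0.65 | 0.04 |
| 75/5/20 vs 75/20/5 | 0.05 | 0.05–0.09 | 0.38–0.77 |

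No outcome has the best power in both patterns.

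**The case against.** **An outcome is implied.** The Background speaks of closing the leak, closure comes first in the list of rates, and suitable data are collected. A reader might infer from the bare endpoint that the study has no efficacy outcome at all; the documents do not support that. What stands is that none of the candidates is chosen.

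**The inflation depends on a reading.** The sentence on rates could mean one test on the whole table, which does not inflate the error. It could also mean a before-after comparison, since it follows the mention of initial and follow-up measurement. The words "Comparison analysis between groups will be made using Kruskal-Wallis tests for nonparametric data sets as appropriate" leave some freedom too. So a reader who concludes that the plan definitely doubles its error rate goes too far. But the text rules out none of the readings, and the freedom selects no outcome.

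**The time point is not contradictory.** It is tempting to set 45-day imaging against a TEE time in months and call this an inconsistency. Recording the actual scan time is compatible with requiring a 45-day scan. The gap is only that no window is stated and the scan is not tied to the endpoint.

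**The study is retrospective and modality was chosen by clinical judgement.** Confounding may matter more than multiplicity, so neither 5% nor 10% is the true error rate. That stands as a limit on what the correction achieves. It is not a reason to leave the outcome open.

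**The analysis may be finished.** The plan mixes tenses and says "All analyses were performed using SPSS Statistics". If results have been seen, pre-specification cannot be restored and the remedy is mainly honest labelling.

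**Conclusion.** The point holds as a specification gap: no primary efficacy outcome, scan window or pairwise rule is designated, and the only named test cannot answer the objective of comparing each modality. On the per-category reading, the chance of at least one false positive is about 9% to 12%, against about 4% to 5% for one outcome with gated pairwise tests. These figures rest on assumed splits and arm sizes and on no true difference. End-of-procedure success and leak size in mm are not counted in them.

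A reader might also infer that 160 patients is the wrong number, or that naming one outcome would make the comparison of modalities sound. The documents give no basis for the first. The second fails because the comparison remains unadjusted for operator choice.

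**What to change.** In the Statistical Analysis section, before modalities are compared:

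1. Name one primary efficacy outcome. Complete closure at the follow-up imaging required by the Exclusion Criteria fits the stated aim best. The investigators may choose clinically significant leak or the ordered category instead, but only one.
2. State the mm boundaries of the categories, an acceptable scan window around 45 days, and which scan counts if there are several.
3. Run one three-group test at two-sided 0.05. Only if it is significant, run the three pairwise tests, each on the two arms concerned and each at 0.05.
4. Report the other categories as proportions with 95% confidence intervals, without efficacy claims.
5. If outcome data have already been seen, label the analysis as specified after data collection.

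**Cost.** No new data are needed, but some nominally significant p-values are lost. For 60/35/5 vs 80/15/5, with the differing arm the worse one, the chance that any of three tests is significant is 0.65–0.80, against 0.52–0.69 for closure alone. Closure has almost no power if modalities differ only in how residual leaks divide between minimal-mild and clinically significant, so the investigators must decide which difference matters most. The change corrects multiplicity only, not confounding.
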